### 16.1.4. SOLICITED AND INJECTION SITE ADVERSE EVENTS (AEs)

In the database all AEs were reported as either solicited or unsolicited, however the database categorization will not be used to report AEs as either solicited or unsolicited. All AEs will be assigned as either solicited or unsolicited based on the PT (refer to APPENDIX 3: Solicited and Injection Site Adverse Event (AE)) and post-vaccination reporting window (refer to Section 16.1.9: Adverse Event (AE) Post-vaccination Reporting Window for a description of the post-vaccination reporting windows).

Local and systemic solicited AE incidence tables will be presented as follows:

- Solicited AE category (local, systemic).
- PT (descending frequency of total number of participants with events reported within each solicited AE category).

The following incidence tables will be presented by PT only:

- Incidence of solicited AEs.
- Incidence of related solicited AEs.
- Incidence of related solicited AEs by dose at onset (refer to Section 16.1.8: Adverse Event (AE) Dose at Onset (Most Recent Vaccination) for details on the derivation of dose at onset):
  - o Number and percentage (%) of participants with AEs summarized by solicited AE category and PT.

---

Document: Aeras\_C-040-404\_SAP\_V2\_0  
Author: [name]

Version Number: 2.0  
Version Date: 29SEP2017

Template No: CS\_TP\_BS016 – Revision 3  
Effective Date: 01May2012

Reference: CS\_WI\_BS005

- o Includes all solicited AEs within the post-vaccination reporting window (refer to Section 16.1.9: Adverse Event (AE) Post-vaccination Reporting Window for details on the derivation of the post-vaccination reporting window).
- o BCG treatment group will only include Dose 1 at onset AEs.
- Incidence of solicited AEs per cohort and dose at onset (refer to Section 16.1.8: Adverse Event (AE) Dose at Onset (Most Recent Vaccination) for details on the derivation of dose at onset):
  - o Number and percentage (%) of participants with AEs summarized by solicited AE category and PT.
  - o Includes all solicited AEs within the post-vaccination reporting window (refer to Section 16.1.9: Adverse Event (AE) Post-vaccination Reporting Window for details on the derivation of the post-vaccination reporting window).
  - o BCG treatment group will only include Dose 1 at onset AEs.
- Incidence of local solicited AEs by severity and dose at onset:
  - o Number and percentage (%) of participants with AEs summarized by solicited AE category and PT.
  - o Includes all local solicited AEs within the post-vaccination reporting window (refer to Section 16.1.9: Adverse Event (AE) Post-vaccination Reporting Window for details on the derivation of the post-vaccination reporting window).
  - o BCG treatment group will only include Dose 1 at onset AEs.
  - o This table will be repeated for systemic solicited AEs and related systemic solicited AEs.

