There is considerable experience with BCG vaccine, which is licensed in South Africa for prevention of TB in children and adults. Local and systemic reactogenicity in various populations is well described (FitzGerald 2000; Hoft et al 1999; Lotte et al 1984; Nicol et al 2002). Injection site and regional complications, such as extensive local ulceration, local subcutaneous abscesses, and suppurative lymphadenitis, occur in less than 1 per 5 million vaccinations. Induration and redness of the skin at the site of intradermal BCG vaccination typically develops within several days and represents a normal response to BCG vaccination. The induration gradually resolves over several days and is followed by a small local superficial ulcer. The ulcer opens and drains for 4 weeks on average, and spontaneously heals within 2-3 months, usually leaving a small scar. A brief period of minor, asymptomatic enlargement of the regional cervical and axillary lymph nodes (< 1 cm) is common. Systemic adverse events due to BCG occur very infrequently. Fever, headache and non-injection site cutaneous manifestations occur in less than 1% of vaccinees. Severe systemic adverse events, such as osteitis and disseminated BCG disease, are rare (about 1 per 5 million vaccinations) and usually occur in immune-compromised infants. Severe local or systemic complications of BCG would not be expected in the healthy, HIV-uninfected, *Mtb* uninfected adolescents to be recruited in this trial.

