**Table 3-4 Adverse Event Collection Periods**

Type of Event	Collection Period
Unsolicited adverse events	28 days post each vaccination a
Solicited adverse events	7 days post each vaccination (with diary cards to be used for 7 days after each vaccination for Safety & Immunogenicity Cohort only)
Solicited and unsolicited injection site reaction adverse events	BCG Group: 84 days post vaccination AERAS-404/Placebo Groups: 28 days post each vaccination a
Serious adverse events, adverse events of special interest, and SUSARs	Entire study period
a. Adverse events will be collected through the end of the study visit window for each adverse event collection period (i.e., 28 days after each vaccination + 5-day window = 33 days)	

For this study, solicited adverse events to be collected include the following: pain, redness and swelling at the site of injection; fever; myalgia; arthralgia; fatigue; headache; anorexia; hives; and chills. Solicited injection site reaction adverse events include (in addition to pain, redness, and swelling) ulceration, drainage, and axillary lymphadenopathy. Solicited adverse events of local injection site reactions (i.e., pain at injection site, redness at injection site, swelling at injection site, ulceration at the injection site, or drainage at the injection site) will be considered causally related to study injection (adverse reaction). Adverse events of special interest (see Appendix D) will be collected passively during participant safety evaluations.

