## 5.7 Solicited Adverse Events and Injection Site Reactions

Solicited adverse events are events the subject is specifically asked about. These adverse events are commonly observed soon after receipt of vaccines. For this study, solicited adverse events to be collected include: pain, redness and swelling at the site of injection; fever; myalgia; arthralgia; fatigue; headache; anorexia; hives; and chills. Solicited injection site reaction adverse events include (in addition to pain, redness, and swelling) ulceration, drainage, and axillary lymphadenopathy. Solicited adverse events of local injection site reactions (i.e., pain at injection site, redness at injection site, swelling at injection site, ulceration at injection site, or drainage at injection site) will be considered causally related to study vaccine (adverse reaction).

**The reporting period during which *solicited* adverse events will be evaluated is specified in Section 3.** The solicited adverse event reporting period begins with the day of vaccination. All subjects in the Safety & Immunogenicity cohort will be provided a diary card to record temperature and information regarding occurrences of these specific events for the 7 days post-vaccination (see further details in Section 5.16).

Adverse events and solicited adverse events including assessment of local injection site reactions will be assessed by the investigator for severity, causal relationship to the study vaccine, possible etiologies, and whether the event meets criteria as a serious adverse event (and therefore requires immediate notification to the medical monitor).

Presence of ulceration and/or scarring at the site of injection and axillary lymphadenopathy of the injection arm(s) are considered to be adverse events that are causally related to the study vaccine and are of special interest. Site of injection ulceration (including presence of drainage) and axillary lymphadenopathy will be actively evaluated during through Day 84. These events will be recorded on the Adverse Event CRF as applicable.

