## 16.2. INJECTION SITE REACTION ASSESSMENT

Injection site reaction assessments will be presented for the Safety analysis set.

The following injection site reaction assessment listing is planned for presentation:

- Injection site reaction assessment.

The following injection site reaction variables will be collected throughout the study on the eCRFs:

- Date and time of assessment.
- Injection site reaction assessment:
  - o Pain.
  - o Redness.
  - o Swelling.
  - o Ulceration.
  - o Drainage.
  - o Abnormality photo taken.
  - o Axillary lymphadenopathy.

Document: Aeras\_C-040-404\_SAP\_V2\_0

Author: [name]

Version Number:

2.0

Version Date:

29SEP2017

Template No: CS\_TP\_BS016 – Revision 3

Reference: CS\_WI\_BS005

Effective Date: 01May2012

Copyright © 2012 Quintiles Transnational Corp. All rights reserved.

The contents of this document are confidential and proprietary to Quintiles Transnational Corp. Unauthorized use, disclosure or reproduction is strictly prohibited.

- Present:
  - o Yes:
    - Measurement (mm) for relevant assessments.
  - o No.

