### APPENDIX 3. SOLICITED AND INJECTION SITE ADVERSE EVENT (AE)

#### PREFERRED TERMS AND CODES

Relevant Treatment Group	Solicited or Injection Site AE	Solicited AE Category	Preferred Term	Preferred Term Code
Placebo H4:IC31 BCG	Solicited AE	Systemic	Pyrexia	10037660
			Myalgia	10028411
			Arthralgia	10003239
			Fatigue	10016256
			Headache	10019211
			Decreased appetite	10061428
			Urticaria	10046735
			Chills	10008531
BCG	Injection site AE	Local	Lymphadenopathy	10025197
			Vaccination site pain	10068879
			Vaccination site erythema	10059079
			Vaccination site swelling	10069620
			Vaccination site ulcer	10069621
Placebo H4:IC31	Injection site AE	Local	Vaccination site discharge	10069560
			Injection site pain	10022086
			Injection site erythema	10022061
			Injection site swelling	10053425
			Injection site ulcer	10022105
			Injection site discharge	10065600

Document: Aeras\_C-040-404\_SAP\_V2\_0

Author: [name]

Version Number:

2.0

Version Date:

29SEP2017

Template No: CS\_TP\_BS016 – Revision 3

Reference: CS\_WI\_BS005

Effective Date: 01May2012

Copyright © 2012 Quintiles Transnational Corp. All rights reserved.

The contents of this document are confidential and proprietary to Quintiles Transnational Corp. Unauthorized use, disclosure or reproduction is strictly prohibited.

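### SAP Appendix 3 identifies the solicited lymph-node reaction by a preferred term with no anatomical site, whereas the protocol solicits axillary lymphadenopathy of the injected arm

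*SAP*

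**What the plan says.** **Protocol.** Section 3.6.3.3 lists the solicited injection-site reactions as pain, redness and swelling plus "ulceration, drainage, and axillary lymphadenopathy". Section 5.7 narrows the node event further: "axillary lymphadenopathy of the injection arm(s) are considered to be adverse events that are causally related to the study vaccine". It also calls these events of special interest and has them actively evaluated through Day 84. Neither section restricts this to one treatment arm.

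**SAP.** Section 16.1.4 states that "the database categorization will not be used to report AEs as either solicited or unsolicited". It replaces the flag with a rule: "All AEs will be assigned as either solicited or unsolicited based on the PT" and on the reporting window, pointing to 16.1.9 "for a description of the post-vaccination reporting windows". The terms are in Appendix 3, where the only lymph-node entry is "Lymphadenopathy". Neither 16.1.4 nor Appendix 3 adds a condition on site or side.

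**Data collected.** SAP 16.2 has "Axillary lymphadenopathy" as its own yes/no item in the injection-site assessment, but plans only a listing of it. The verbatim adverse event term (SAP 16.1) and the injected arm, left or right (SAP 13), are also on the eCRF.

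**The concern.** The term the SAP uses is wider than the event the protocol defines. The site's own classification, which could have separated axillary nodes from others, is overridden, and neither the assessment item nor the verbatim term is brought in to replace it. A node remote from the injection could then be reported as a solicited vaccine reaction.

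Safety is a primary objective, and the protocol singles out axillary nodes of the injected arm. The solicited tables should report that event, and the unsolicited tables should keep the rest. No efficacy result is involved.

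**Working it through.** The plan states no figure on this point, so the check sets the rules side by side and follows test cases through them.

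**Step 1. The two definitions.**

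| | Protocol 3.6.3.3, 5.7 | SAP 16.1.4, Appendix 3 |
|---|---|---|
| Site | Axilla | Not specified |
| Side | Injected arm(s) | Not specified |
| Arms | No restriction | Depends on the Appendix 3 row |
| Window | BCG 84 days; other arms 28 days after each dose | Depends on the category of the row |

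**Step 2. The Appendix 3 row.** In the extracted text, Lymphadenopathy heads the block for BCG, injection site, Local. But Vaccination site discharge falls at the start of the Placebo/H4:IC31 block, although the other vaccination-site terms are under BCG. The labels may be displaced by one row, which would put Lymphadenopathy next to the all-arm Systemic block. Arm and category are therefore uncertain. The absence of a site is not.

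**Step 3. Two test cases under each reading.** By the protocol definition, an inguinal node on Day 5 is unsolicited, and an axillary node on the injected side on Day 20 is a solicited injection-site reaction. Systemic events have a 7-day window (SAP 16.1.9).

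| Reading of the row | Inguinal node, Day 5 | Axillary node, injected side, Day 20 |
|---|---|---|
| BCG only, Local | BCG: local solicited (wrong) | BCG: correct; H4:IC31 and Placebo: not on the local list (wrong) |
| All arms, Local | Local solicited in all arms (wrong) | Correct |
| All arms, Systemic | Systemic solicited in all arms (wrong) | Outside 7 days, so not solicited (wrong) |

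Every reading misclassifies at least one case. An axillary node on the uninjected side goes the same way as the inguinal node.

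**Step 4. Tables affected.** The overview rows for solicited events (SAP 16.1.2) and, in 16.1.4, the incidence of solicited events, the version by cohort and dose, and local solicited events by severity and dose are not filtered on relatedness. The last has no related-only repeat; that is planned for systemic events only. Related-event tables follow the reported relationship (SAP 16.1.2.2), so a node judged unrelated stays out of them.

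**Step 5. Does the longer BCG window matter?** The local windows are 84 days for BCG and 2 × 28 = 56 days in the two-dose arms. But a groin node is not an injection-site reaction. Protocol Table 3-4 collects unsolicited events for 28 days after each vaccination, extended by the visit window to 28 + 5 = 33 days. Protocol Table 3-1 and Appendix A show no general unsolicited collection at the BCG Day 70 and Day 84 visits. Planned collection of non-serious remote nodes is thus one 28-day period in BCG and two in the other arms. The 84-day window does not lengthen it.

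**Step 6. Size.** A count needs the rate of non-axillary or contralateral lymphadenopathy, which neither document gives. The scale per event is all that follows: one misclassified participant moves a row by 1/330 = 0.3 percentage points in a full arm, and by 1/30 = 3.3 points in one arm of the Safety and Immunogenicity Cohort.

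**The case against.** The strongest case against is that this is a wording gap in one row of a table whose extraction is unreliable, with little consequence. If the row is Systemic, only the first 7 days are exposed to the remote-node error. Nodes accompanying another illness may be recorded under that diagnosis, since Protocol 5.3 asks for a recognized medical term or diagnosis, and would then never be coded to Lymphadenopathy. Solicited status does not make an event related in the SAP tables, and separate related-solicited tables are planned. The axillary item is visible in its own listing.

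Most of this stands, and it keeps the point small. It does not remove it: the table in Step 3 shows a wrong classification whichever way the row is read, and several planned tables have no relatedness filter.

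A reader might also infer that neck nodes in BCG recipients would be wrongly counted as vaccine reactions. The documents do not support calling them unrelated: Protocol 1.6 says that after BCG "enlargement of the regional cervical and axillary lymph nodes (< 1 cm) is common". Cervical nodes are not the event solicited in 5.7, but the clear examples are groin or other remote nodes and contralateral axillary nodes.

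**Conclusion.** The point holds in a limited form. Under SAP 16.1.4 and Appendix 3, a remote or contralateral node coded to Lymphadenopathy within the applicable window is counted as solicited and leaves the unsolicited tables. Related-event tables are less affected.

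This assumes that axillary and other nodes can both be coded to the listed term, which names no site; the documents do not show the coding in practice. The number of events cannot be estimated from the documents.

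A reader might infer that the 84-day BCG window inflates local reactions in that arm relative to the others. The collection schedule does not support that (Step 5), and no such between-arm inflation should be claimed. An imbalance from another source is possible but conditional. If the row really is BCG-only, true axillary nodes in H4:IC31 and Placebo are missing from the local list. If it is Systemic, the 7-day window drops later axillary nodes that the protocol solicits. Only the source PDF can settle which applies.

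Priority is low: it affects how one safety event is tabulated.

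**What to change.** First confirm in the source PDF which arms and category the Lymphadenopathy row of Appendix 3 carries. Then state in SAP 16.1.4 and Appendix 3:

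- Lymphadenopathy is a local solicited event, in all three arms and with each arm's local window, only when the injection-site assessment records axillary lymphadenopathy for that injection, or the verbatim term is axillary on the injected side.
- All other lymphadenopathy is reported as unsolicited.
- Where the assessment and the verbatim term disagree, the case is settled in a review of verbatim terms before unblinding, blinded to treatment where possible.

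The side must be matched to the dose, because Protocol 3.5 gives the second H4:IC31 or Placebo injection in the opposite arm.

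The cost is one derivation rule and a review of the verbatim terms coded to Lymphadenopathy. The assessment item, verbatim term and injected arm are already on the eCRF, so no new data are needed.

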#### 16.1.5. SERIOUS ADVERSE EVENTS (SAEs)

An SAE is any AE for which serious event is indicated as ‘yes’ on the Adverse Event eCRF.

The following listing is planned for presentation by treatment group:

- SAEs.
- SAEs with an outcome of death.

The following incidence table is planned for presentation by SOC and PT:

- Incidence of serious adverse events by dose.
- Incidence of serious adverse events with outcome of death.

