### 3. STUDY DESIGN

#### 3.1. GENERAL DESCRIPTION

A Phase II, randomized, 3-arm, placebo-controlled, partially blinded clinical trial that was conducted in 990 healthy HIV-uninfected, QFT-GIT negative, previously BCG vaccinated adolescents. Participants were recruited from high schools or directly from the community.

Participants were enrolled in two sequential cohorts:

- Safety and Immunogenicity Cohort:
  - o First 90 participants (30 from each arm).
  - o More intensive collection of safety data.
  - o Selected immunogenicity assays (including whole blood intracellular cytokine staining [ICS]).
  - o Data reviewed by the data monitoring committee (DMC), principal investigator and local medical monitor.
- Correlates Cohort:
  - o Remaining 900 participants.

All 990 participants in the study were evaluated for:

- Safety outcomes.
- Biomarker outcomes.
- Prevention of *Mtb* infection.

Within each cohort, participants were randomized in a 1:1:1 ratio to one of the following treatment groups:

- H4:IC31:
  - o 15 mcg H4/500 nmol IC31.
  - o Two doses (administered on Day 0 and Day 56).
  - o Intramuscular injection.
- Placebo:
  - o Saline volume equivalent to the H4:IC31 injection.
  - o Two doses (administered on Day 0 and Day 56).
  - o Intramuscular injection.

---

Document: Aeras\_C-040-404\_SAP\_V2\_0

Author: [name]

Version Number:

2.0

Version Date:

29SEP2017

Template No: CS\_TP\_BS016 – Revision 3

Reference: CS\_WI\_BS005

Effective Date: 01May2012

Copyright © 2012 Quintiles Transnational Corp. All rights reserved.

The contents of this document are confidential and proprietary to Quintiles Transnational Corp. Unauthorized use, disclosure or reproduction is strictly prohibited.

- BCG:
  - o 2-8 x 10^5 CFU.
  - o One dose (administered on Day 0).
  - o Intradermal injection.

Randomization to the H4:IC31 and Placebo treatment groups was double-blinded. Since BCG causes a recognizable local injection site reaction, the BCG revaccination treatment group was not blind. Laboratory staff performing QFT-GIT, immunogenicity and correlates assays were blinded to all three treatment groups. Planned randomization of participants is specified in Table 1: Planned Enrollment by Treatment Group and Cohort, below:

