## 13.1. DERIVATIONS

Based on the aforementioned the following variables, as presented in the planned TLF shells, will be derived:

- Participants who received all scheduled vaccinations:
  - o Yes:
    - For BCG treatment group participants if Day 0 study vaccination date is available.
    - For H4:IC31 or Placebo treatment group participants if Day 0 and Day 56 study vaccination dates are both available.

---

Document: Aeras\_C-040-404\_SAP\_V2\_0

Author: [name]

Version Number:

2.0

Version Date:

29SEP2017

Template No: CS\_TP\_BS016 – Revision 3

Reference: CS\_WI\_BS005

Effective Date: 01May2012

Copyright © 2012 Quintiles Transnational Corp. All rights reserved.

The contents of this document are confidential and proprietary to Quintiles Transnational Corp. Unauthorized use, disclosure or reproduction is strictly prohibited.

- o No:
  - For BCG treatment group participants if Day 0 study vaccination date is not available.
  - For H4:IC31 or Placebo treatment group participants if Day 0 and/or Day 56 vaccination dates are not available.
- Study day of the Day 56 vaccination:
  - o Calculated relative to Day 0 vaccination (refer to Section 6.1: Reference Start Date and Study Day).
- Participants who received the second vaccination within the protocol-defined window:
  - o This is only applicable to the H4:IC31 and Placebo participants.
  - o The allowable window for the Day 56 visit is 56-2 days until 56+14 days from the Day 0 vaccination.
  - o Yes:
    - Study day of the Day 56 vaccination  $\geq 54$ .
  - AND
  - Study day of the Day 56 vaccination  $\leq 70$ .
  - o No:
    - Study day of the Day 56 vaccination  $< 54$ .
  - OR
  - Study day of the Day 56 vaccination  $> 70$ .

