#### **16.1.8. ADVERSE EVENT (AE) DOSE AT ONSET (MOST RECENT VACCINATION)**

A dose at onset will be assigned for all AEs and is defined as the most recent dose prior to the onset of the AE:

- Post any dose (combination of the AEs starting after the Day 0 and Day 56 vaccinations).
- Post-dose 1 (AEs starting after the Day 0 vaccination).
- Post-dose 2 (AEs starting after the Day 56 vaccination):
  - o Only applicable to H4:IC31 and Placebo treatment groups.

The assignment of the dose at onset will be based on the following algorithm:

- Calculate the difference in the AE start date (as collected on the Adverse Events eCRF) and all available study vaccination dates (as collected on the Exposure Day 0 and Exposure Day 56 eCRFs):
  - o Days since dose x: (AE start date – study vaccination dose x date [where x= 1 or 2]).
- From the previous calculation, only consider those doses where the days since dose x is  $\geq 0$  and determine the dose (1 or 2) for which the days since dose x (as calculated in the previous step) is a minimum.
- Assign the dose selected in the previous step as the dose at onset as the specific dose determined in the previous calculation.

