#### **16.1.9. ADVERSE EVENT (AE) POST-VACCINATION REPORTING WINDOW**

All SAEs and AESIs will be collected through database lock.

All unsolicited AEs will be collected during the 28-day reporting window following each study vaccination. The reporting window is defined in terms of the relevant scheduled study visit coinciding with the 28-day window following the relevant dose.

Solicited systemic adverse events will be collected during the 7-day reporting window following each study vaccination (diary cards will be used for 7 days following each study vaccination for the Safety and Immunogenicity Cohort only).

Solicited and unsolicited local injection site reaction adverse events will be collected:

- BCG treatment group:
  - o 84-day reporting window following study vaccination.
- H4:IC31 and Placebo treatment groups:
  - o 28-day reporting window following each vaccination.

---

Document: Aeras\_C-040-404\_SAP\_V2\_0  
Author: [name]

Version Number: 2.0  
Version Date: 29SEP2017

Template No: CS\_TP\_BS016 – Revision 3  
Effective Date: 01May2012

Reference: CS\_WI\_BS005

Refer to Table 4: General Adverse Event (AE) Post-vaccination Reporting Windows below for the relevant post-vaccination reporting windows as defined in terms of scheduled study visits:

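### SAP 16.1.5 splits SAE incidence by dose, so the post-dose-1 period is about 8 weeks in the placebo and H4:IC31 arms but all of follow-up in the BCG arm, and BCG cannot be compared with either arm on that figure

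*SAP*

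**What the plan says.** SAP 16.1.5 lists two SAE incidence tables by SOC and preferred term: "Incidence of serious adverse events by dose", and one for SAEs with a fatal outcome. It also plans SAE listings by treatment group.

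The split by dose follows SAP 16.1.8: "A dose at onset will be assigned for all AEs and is defined as the most recent dose prior to the onset of the AE". The algorithm there asks only that days since the dose be zero or more, then takes the nearest dose; it sets no maximum. The post-dose-2 category is marked "Only applicable to H4:IC31 and Placebo treatment groups". A post-any-dose category is also defined.

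On the collection period, SAP 16.1.9 states: "All SAEs and AESIs will be collected through database lock". Table 4 of that section repeats this for all arms and doses. The other event types have fixed windows: 28 days for unsolicited AEs, 7 days for systemic solicited AEs, and 28 days (84 for BCG) for local solicited AEs.

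SAP 3.1 gives the schedules: Day 0 and Day 56 for H4:IC31 and placebo, Day 0 only for BCG. SAP 13.1 sets the tolerance for the second dose: "The allowable window for the Day 56 visit is 56-2 days until 56+14 days from the Day 0 vaccination", that is, Day 54 to Day 70.

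**The concern.** Together these rules make one label describe two different periods. An SAE on Day 300 counts as post-dose 2 in a placebo participant who had both injections, and as post-dose 1 in a BCG participant. Placed next to each other, the post-dose-1 percentages would suggest an SAE excess on BCG that comes only from length of observation. Within a two-dose arm, post-dose 2 would likewise look far worse than post-dose 1.

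Safety of BCG revaccination is part of a primary objective, and BCG is the unblinded arm, so an apparent excess could readily be taken as real. Apart from the table of deaths, this is the only SAE-specific incidence table by SOC and preferred term, so it is where a reader would look for the kinds of SAE seen in each arm. The SAP text plans no person-time SAE rate, and no common post-dose window for SAEs, that would expose the difference.

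**Working it through.** **The plan's own SAE figure.** Protocol 7.6 says that no SAE among 330 gives an exact upper 95% bound of 1%. This reproduces: 1 − 0.05^(1/330) = 0.90% one-sided and 1 − 0.025^(1/330) = 1.11% two-sided. It concerns a whole arm, not a dose period. The documents give no by-dose SAE figure and no expected SAE rate.

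**Inputs.**
- Dose 2 on Day 56, allowed Day 54 to 70 (SAP 3.1 and 13.1).
- Month 24 visit at Day 672 (SAP Appendix 8), the last visit for non-converters.
- Converters after Day 84 leave 168 days after conversion. Day 84 converters leave at Day 168 (BCG) or Day 224 (two-dose arms) (Protocol Tables 3-1 and 3-2).
- Loss 7% per year; conversion 10% per year, with 17% also cited (Protocol 7.6).
- 330 per arm.
- Assumptions, not in the documents: a constant SAE hazard equal in all arms; SAE rates of 1%, 2% and 5% per year; 0% to 5% of two-dose participants missing dose 2.

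**Step 1: nominal ratio.** With equal constant hazards, the ratio of expected post-dose-1 SAEs equals the ratio of time assigned to post-dose 1:
- dose 2 on Day 56: 672/56 = 12.0
- dose 2 on Day 54: 672/54 = 12.4
- dose 2 on Day 70: 672/70 = 9.6

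Within a two-dose arm, post-dose 2 is (672 − 56)/56 = 11 times as long as post-dose 1. With only 15 study months of follow-up (420 days, the minimum median at the primary analysis in SAP 4.2), the BCG ratio would be 420/56 = 7.5.

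**Step 2: loss and conversion.** Follow-up was simulated with these rates, detection at the scheduled visits and the exit rules above. At 7% loss and 10% conversion, mean BCG follow-up is 609.8 days and mean post-dose-1 time in a two-dose arm is 55.7 days: 609.8/55.7 = 10.9. At 17% conversion the ratio is 10.7.

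**Step 3: missed second doses.** A participant who misses dose 2 stays in post-dose 1 to the end. With a share m missing and no attrition, the ratio is 672/(56 + 616m); at m = 5% this is 672/86.8 = 7.7. With the Step 2 attrition (10% conversion):

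| Missing dose 2 (assumed) | Ratio |
|---|---|
| 0% | 10.9 |
| 1% | 9.9 |
| 3% | 8.4 |
| 5% | 7.3 |

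**Step 4: participants with at least one SAE.** P(t) = 1 − exp(−λt), with λ = −ln(1 − r)/365.25, full follow-up and no missed doses:

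| Assumed r per year | BCG post-dose 1 (672 days), of 330 | Two-dose arm post-dose 1 (56 days), of 330 | Ratio |
|---|---|---|---|
| 1% | 6.0 | 0.5 | 11.9 |
| 2% | 12.0 | 1.0 | 11.8 |
| 5% | 29.7 | 2.6 | 11.5 |

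The counts depend on the assumed rate; the ratio hardly does.

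**Step 5: equal periods.** Over all follow-up (post any dose), the BCG to two-dose ratio of mean follow-up is 672/672 = 1.00 nominally and 609.8/611.1 = 0.998 with attrition. The artefact disappears.

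**The case against.** The strongest reply is that the SAP already provides sound comparisons and that this table carries little weight. Much of that stands.

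- A reader might infer that only the post-any-dose figures can be compared between arms. The documents do not support this. H4:IC31 and placebo share one schedule, so they are comparable in both dose categories. The apparent rise after dose 2 would also appear under placebo, which identifies it as follow-up time.
- Post any dose covers the same period in every arm. The overview table in SAP 16.1.2 has an SAE row by arm with counts, percentages and confidence intervals. The SAE listings are unaffected.
- A reader might infer that the primary safety conclusion is compromised. Protocol 7.5.1 bases it on solicited and unsolicited AEs, promises listings for SAEs, and makes per-vaccination summaries optional. No test or decision rule uses this table, and the DMC's Day 7 and Day 84 reviews ran under a separate SAP.
- SAP 8 leaves layout to the table shells, which are not available here. A footnote or a BCG-specific layout cannot be excluded. SAP 16.1.4 does note that BCG has dose 1 only in the solicited by-dose tables.

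These points limit the reach of the problem without removing it. The overview row gives totals without event types. The general AE table by SOC and preferred term does not show SAEs separately. Nothing in the SAP text tells the reader that BCG's post-dose-1 figure covers the whole study.

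**Conclusion.** The point holds within limits. Followed as written, SAP 16.1.5, 16.1.8 and 16.1.9 give a post-dose-1 SAE figure for BCG that cannot be set against the same figure for placebo or H4:IC31. With identical arms, the expected excess is roughly 7 to 12 times. A flat twelvefold excess is a tempting reading, but 12 is the nominal value, with everyone followed to Day 672 and given dose 2 on Day 56. About 11 fits the protocol's own loss and conversion rates, and the lower end needs up to 5% missed second doses, an assumed share. All of these figures rest on a constant SAE hazard.

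The only other distorted contrast is post-dose 1 against post-dose 2 within a two-dose arm. This is a reporting fault in a descriptive table. It is worth correcting because the table is the main SAE display by event type.

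**What to change.** In SAP 16.1.5, make the SOC and preferred-term SAE table a whole-study table by arm, counting each participant once and not split by dose. Person-years are optional, since expected follow-up is nearly equal between arms.

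If a by-dose split is kept, either limit it to a common window after each dose (for example the 28 days already used for unsolicited AEs) or use the same Day 0–55 and Day 56-onward periods in all three arms. Apply the same rule to SAEs and AESIs wherever they enter the other by-dose AE tables (SAP 16.1.2 and its subsections).

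The cost is a change of SAP wording and a small amount of re-programming from onset and vaccination dates already collected. If a post-dose window is chosen, SAEs outside it will appear only in the whole-study table.
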